## Study Synopsis

[figure not shown]
Full Title	Is there a Relationship between Memory for Past Events and Motivation for Future Activities?
Short Title/Acronym	The Relationship between Autobiographical Memory and Motivation
Protocol Version number and Date	V4 14/11/16
Study Duration	27 months
Study Design	A cross-sectional, experimental study with a pilot intervention study component.
Sponsor/Co-sponsors	South London and Maudsley NHS Trust
Chief Investigator	[name]
REC number	
Primary objective	Cross sectional associations between autobiographical episodic memory, motivation, experience of pleasure and depression will be examined.
Secondary objective (s)	An intervention study will be conducted to further explore the potential causal role of autobiographical episodic memory in experiential negative symptoms. This will use a brief intervention targeting memory flexibility which is hypothesised to improve pleasure and motivation outcomes.
Number of Subjects	35-40
Main Inclusion Criteria	A diagnosis of non-affective psychosis (as determined by medical records). Aged 18-65yrs. A score of at least 18 on the Clinical Assessment Interview for Negative Symptoms. A good command of the English language.
Statistical Methodology and Analysis	Correlational analyses will be conducted to examine the relationships hypothesised in Part 1 of the study. The ratings provided before and after the study will be analysed in a between-groups ANOVA to assess the effect of the brief intervention on mood, motivation, anticipatory pleasure and self-efficacy beliefs.

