## **3. Sample Size, Statistics, Selection and Withdrawal of Subjects**

People with a diagnosis of non-affective psychosis aged 18 - 65yrs will be recruited from local community mental health teams and inpatient wards within South London and Maudsley NHS Trust. Further eligibility criteria for the study are a score of at least 18 on the experiential subscale of the Clinical Assessment Interview for Negative Symptoms to ensure at least a moderate level of current negative symptomatology.

A power analysis conducted in GPower Software (version 3.2) with power at 0.8 and  $\alpha = 0.05$  found a sample size of 32 would be sufficient to replicate a correlation with a medium effect size of 0.43 between memory specificity and negative symptoms reported by Harrison and Fowler (2004). To account for drop-outs a sample size of 35-40 will be recruited, if there are few drop-outs this will also increase the power of the study. This sample size with a randomisation ratio of 2:1 is sufficient to detect an F statistic of 0.43 with power at 0.8 and 0.53 with power at 0.9.

There will be three recruitment routes in the study;

1. If recruited through a clinical team then the participant will first be approached by a member of their care team to introduce the study. If they indicate that they are happy to consider the project and give verbal consent for the researcher to contact them then they will be provided with the information sheet. The researcher will then contact them again after at least 24 hours to discuss their potential participation.
2. If recruited through CRIS then potential participants will first be approached by the researcher. This will be done by phone or letter, depending on the preference indicated by the potential participant.
3. If recruited through a recruitment poster then the participant will contact the researcher using the details provided on the poster.

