### **Part 2 Experimental Study**

## **Outcomes**

The participants will be asked to rate the following items before and after their participation in either the intervention or control condition. These are rated on 100-point visual analogue scales from 1 “Not at All” to 10 “Very Much So”. These are similar to those used in experience sampling studies where these repeated measures have been shown to be reliable and valid (Gard, Kring et al. 2007, Oorschot, Lataster et al. 2011, Gard, Sanchez et al. 2014).

- 1) Right now I feel [enthusiastic, satisfied, relaxed, cheerful]
- 2) Right now I feel [down, guilty, anxious, annoyed]
- 3) How likely the event is to happen again.
- 4) How able they would feel to engage in the future event.
- 5) How enjoyable the future event would be.

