### **Intervention Condition**

In contrast to the baseline task participants will be asked to generate narratives for positive events they think may happen again in the future.

The autobiographical memory task described previously will also be adapted to include the following intervention components:

- 1) An animated video with people explaining how they find memory helpful in deciding what they do and don't want to do in the future, and how this is motivating.
- 2) Cues provided during the generation of the narrative as follows:
  - a. Why did you choose this activity? Did this activity give you a sense of achievement? How enjoyable was it?
  - b. Where is it/ When is it/Who is there?
  - c. Sight/Hear/Smell/Sound/Taste.
- 3) A reminder of the link between memory and anticipation
  - a. Would you do this activity again? Why/why not?
- 4) A reminder of the links between this memory/event and others.
  - a. Can you link this to other events?
  - b. What does this memory tell us about you as a person?

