### **Procedure**

Part 1: Participants will complete the baseline autobiographical memory task which involves recalling 1 positive and 1 negative event which will be audio-recorded and coded by two independent raters. Then participants will complete the two subtests of the Wechsler Abbreviated Intelligence Scale - verbal fluency and letter-number sequencing which assess working memory. Two questionnaires that assess depression symptoms and negative thinking (Beck Depression Inventory and Dysfunctional Attitudes Scale) will then be completed by the participant. Finally, three interviews assessing symptoms and functioning will be conducted by the researcher (CAINS, Time Use Survey and Scale for the Assessment of Positive Symptoms (SAPS). This session should last approximately 1.5-2hrs.

Part 2: After Part 1 the participants will be randomized to the intervention or control group using a 2:1 ratio and the “sealed envelope” online software. This will be done by the Chief Investigator who will record the randomisation process and outcome. At the start of the Part 2 session the participants will be asked to select a positive event to describe. They will then complete the visual analogue scales assessing positive and negative feelings, motivation, anticipatory pleasure and self-efficacy. The participants will then complete either the intervention or control task before repeating the visual analogue scales again. The intervention and control task both involve describing this positive event; the control task with no prompts and the intervention task with prompts and videos encouraging them to include more detail in their recall and to link it to past and future events as well. Participants will do this process for two positive events and this session should last approximately 1 hr. Participants will be asked to complete a brief feedback questionnaire at the end of their participation in the study.

This concludes the participant’s involvement in the research.

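### The Part 2 ANOVA names no tested term, covariate or rule for the two events; ANCOVA on the same ratings would be modestly more precise

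*Combined protocol and SAP*

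**What the plan says.** The Study Synopsis states: "The ratings provided before and after the study will be analysed in a between-groups ANOVA". The outcomes it lists are mood, motivation, anticipatory pleasure and self-efficacy. Section 3 has statistics in its title, but for Part 2 it gives only detectable effects: "This sample size with a randomisation ratio of 2:1 is sufficient to detect an F statistic of 0.43 with power at 0.8", and 0.53 at power 0.9. It does not say which test these refer to.

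On the data collected, the Outcomes section says: "The participants will be asked to rate the following items before and after their participation in either the intervention or control condition". The Procedure in Section 4 sets the order within each event, "The participants will then complete either the intervention or control task before repeating the visual analogue scales again", and adds: "Participants will do this process for two positive events". Each item therefore has four ratings per participant: before and after for event 1, then before and after for event 2. No section says how the four become one comparison.

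The intervention contains elements that are not tied to one event: "An animated video with people explaining how they find memory helpful" and "A reminder of the links between this memory/event and others".

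**The concern.** A between-groups ANOVA of before and after ratings can mean several tests: group-by-time, a group main effect over both times, or a comparison of after-ratings alone. They differ in power, and the choice is open until someone makes it, possibly after seeing the data and across several outcomes.

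Under the natural reading, group-by-time, the before-rating is simply subtracted. ANCOVA estimates how much of it to subtract, and so is usually more precise on the same data. With about 12 controls, precision that needs no new data is worth having.

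The second pair raises a further question. Its before-rating follows the first task, so if any effect of that task persists, a change score for event 2 would subtract it.

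**Working it through.** **Inputs.** From Section 3: alpha 0.05, allocation 2:1, 35-40 participants, detectable effect 0.43. I use N = 36 (24:12) and two-sided tests. Not in the documents, so assumed: rho from 0.3 to 0.9, equal variances, and the carry-over share c. Variances V are in units of the variance of a single rating.

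**The plan's own figure.** Read 0.43 as Cohen's f in a two-group ANOVA with noncentrality N·f². Power at f = 0.43 is then 69.5% at N = 35 and 75.5% at N = 40, not 80%. For f = 0.53 it is 86.1% and 90.4%, so that figure reproduces at N = 40. No variant tried gave both stated figures at one N. The power values below are therefore illustrative; the variance ratios and CI widths do not depend on 0.43. As a standardised difference, d = 0.43/√((2/3)(1/3)) = 0.912.

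**One pair.** The variances are:
- Change score (group-by-time): V = 2(1−rho), 34 df.
- ANCOVA: V = 1−rho², 33 df, times 1+1/(N−4) = 1.031 to allow for chance imbalance.
- Group main effect over both times: effect d/2, V = (1+rho)/2.

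The ratio of ANCOVA to change is (1−rho²)/(2(1−rho)) = (1+rho)/2 before the allowance. The CI half-width is t × √(V(1/24+1/12)). At rho 0.5:
- Change: 2.032 × √(1.00×0.125) = 0.72.
- ANCOVA: 2.035 × √(0.75×1.031×0.125) = 0.63.

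Power uses noncentrality d²/(0.125V), with d taken as the effect on the after-rating. The lower ANCOVA power figure includes the allowance.

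| rho | Half-width, change | Half-width, ANCOVA | Power, change | Power, ANCOVA | Power, main effect |
|---|---|---|---|---|---|
| 0.3 | 0.85 | 0.70 | 0.56 | 0.73-0.75 | 0.34 |
| 0.5 | 0.72 | 0.63 | 0.71 | 0.81-0.82 | 0.30 |
| 0.7 | 0.56 | 0.52 | 0.90 | 0.93-0.94 | 0.27 |
| 0.9 | 0.32 | 0.32 | >0.99 | >0.99 | 0.25 |

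**Two events, four equally correlated ratings, no carry-over.**
- Averaged change: V = 1−rho.
- ANCOVA, average after on average before: the slope is 2rho/(1+rho), and V = (1+rho)/2 − 2rho²/(1+rho) = (1−rho)(1+3rho)/(2(1+rho)).
- ANCOVA, average after on first before only: V = (1+rho)/2 − rho².

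| rho | Average-before ANCOVA ÷ change | With 1.031 allowance | First-before ANCOVA ÷ change (= 0.5+rho) |
|---|---|---|---|
| 0.3 | 0.73 | 0.75 | 0.80 |
| 0.5 | 0.83 | 0.86 | 1.00 |
| 0.7 | 0.91 | 0.94 | 1.20 |
| 0.9 | 0.97 | 1.00 | 1.40 |

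**If a share c of the effect sits in the second before-rating**, and both after-ratings carry the same total effect, the methods keep:
- Averaged change: 1−c/2.
- ANCOVA on the average before-rating: 1−c·rho/(1+rho).
- ANCOVA on the first before-rating: all of it.

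At c = 0.5, averaged change keeps 75%. ANCOVA on the average before-rating keeps 83% at rho 0.5 and 79% at rho 0.7.

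**The case against.** The strongest case is that the planned test, read naturally, is sound. Group-by-time under randomisation is valid, it already uses the before-ratings, and its loss of precision is modest. If ratings within one session correlate near 0.9, there is almost nothing to gain. All of this stands, and it keeps the priority low.

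Three stronger readings are tempting, and the documents do not support them.
- *The plan tests a group main effect over both times.* The low power of that test (0.25-0.34) might suggest a serious flaw. But the synopsis analyses before and after ratings to assess the intervention's effect, which points to group-by-time. The main effect only shows what the wording leaves open.
- *The second before-rating is contaminated.* No section says that an effect persists from one event to the next. Items 3-5 of the Outcomes concern a particular event, and the second pair is about a different one. Carry-over is plausible, given the general video and the linking prompts, but it is an assumption. The arithmetic also assumes that both after-ratings carry the same total effect. If the second task added a full effect to what persisted, each change score would still equal d and nothing would be subtracted.
- *The main analysis should therefore adjust for the first before-rating alone.* That is a trade-off. Without carry-over its variance is 1.20 times the averaged change score's at rho 0.7 and 1.40 times at 0.9. For items 3-5 its covariate would rate event 1 while half the outcome rates event 2. Using only event 1 would discard half the ratings.

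**Conclusion.** The point holds as a matter of specification and modest precision, not of bias. The plan names no tested term, covariate or rule for the two events. Against the natural reading with one pair, ANCOVA narrows the 95% CI half-width from 0.85 to 0.70 SD at rho 0.3, from 0.72 to 0.63 at 0.5 and from 0.56 to 0.52 at 0.7, with essentially no gain at 0.9. With both events averaged and no carry-over, the variance falls by about 25%, 14%, 6% and 0% at rho 0.3, 0.5, 0.7 and 0.9.

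These sizes rest on assumed values of rho, equal variances and, for two events, equal correlations among the four ratings. The unnamed term matters at least as much as the precision: at rho 0.5 the illustrative power runs from 0.30 to about 0.82 across readings that the sentence permits. Part 2 is a secondary pilot component and its natural test is valid, so the priority is low.

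**What to change.** Replace the ANOVA sentence with a participant-level ANCOVA for each outcome. The outcome is the average of the after-ratings over the two events, arm is the factor, and the average of the matching before-ratings is the covariate. Report the adjusted mean difference with its 95% CI. Fix this wording before the data are seen, and say how a participant with only one completed event enters the average.

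Add one sensitivity analysis that adjusts only for the first before-rating, which precedes any task. State alongside it that it has more variance than the averaged change score when rho is above about 0.5 and little carries over, so a wider interval there is not evidence against the main result.

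The cost is one sentence and one degree of freedom for the main analysis, with no new data.

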## 1. Introduction

Schizophrenia-spectrum diagnoses have been shown to be among the top ten causes of disability worldwide (The Schizophrenia Commission 2012). Psychosis can be conceptualised as reflecting two main symptom clusters; positive symptoms which include delusions and hallucinations and negative symptoms which have been defined by the National Institute of Mental Health (NIMH) Consensus according to the dimensions of anhedonia and apathy, avolition and asociality, poverty of speech and blunted affect (Kirkpatrick, Fenton et al. 2006). Negative symptoms appear to play a significant role in outcomes for people with psychosis, as they are associated with poorer social functioning, work/school functioning and activities of daily living (Robertson, Prestia et al. 2014, Marchesi, Affaticati et al. 2015, Menendez-Miranda, Garcia-Portilla et al. 2015). Service users have also identified apathy and low motivation as a priority for recovery (Sterk, Winter van Rossum et al. 2013). Despite this wealth of evidence highlighting the importance of intervening to alleviate negative symptoms the only recommended treatment in the NICE (2014) guidelines is art therapy, although the evidence for its effectiveness is limited. A recent meta-analysis confirmed that available treatments show modest effectiveness at best with many having no effect at all (Fusar-Poli et al. 2014).

Many factor analyses conducted show that negative symptoms are best characterized in two broad categories; *experiential* negative symptoms such as apathy, anhedonia and asociality and *expressive* negative symptoms including poverty of speech and blunted affect (Messinger, Tremeau et al. 2011). Experiential negative symptoms, in particular, low motivation and pleasure, have been strongly linked to worse functioning and outcomes in people with schizophrenia (Fervaha, Foussias et al. 2013). One model that has been proposed for experiential negative symptoms is the Temporal Experience of Pleasure Model (Kring and Caponigro 2010, Kring and Barch 2014) (see Figure 1).

**Figure 1: The Temporal Experience of Pleasure model. Triangles represent pleasure-related processes, ovals represent autobiographical episodic memory and working memory components and rectangles represent motivation and activity**

The Temporal Experience of Pleasure model proposes an important role for memory in the generation of anticipatory pleasure and subsequent motivation and engagement in activity, in particular, episodic memory, which is defined as the memory for autobiographical events that can be explicitly stated. These memories for past personal experiences allow the person to figuratively travel back in time to the event that took place at that particular time and place (Tulving 1972). Autobiographical memory is a related memory system that combines episodes from a person's life with semantic knowledge about the world and the self (Conway and Pleydell-Pearce 2000). The TEP model proposes that during an activity the pleasure being experienced is maintained and then encoded into episodic memory. When the opportunity to repeat this, or a similar activity, is presented the individual retrieves relevant episodic memories and holds these representations online in the working memory (Kring and Caponigro 2010). If there is a failure to either encode the pleasure and activity into memory or retrieve it then this may lead to failure to anticipate pleasure from and then repeat that activity. This model therefore suggests that episodic memory may be an important therapeutic target in the context of the negative symptoms of schizophrenia, however the existing literature is unclear. Several studies report impairments in episodic memory in people with schizophrenia (Berna, Potheegadoo et al. 2016). However, there are mixed findings regarding whether there is a link between these impairments and experiential negative symptoms with some studies reporting an association and others not (Harrison and Fowler 2004, Ricarte, Hernandez et al. 2014, Berna, Potheegadoo et al. 2016). The methodology used across studies to assess memory is relatively consistent, with the autobiographical memory test

(Williams and Broadbent 1986) utilized in the majority of studies. This task may have some limitations due to its reliance on event cue words e.g. "birthday" rather than specific prompting of episodic memories of a particular valence, reducing its ecological validity. It may be more valid to prompt the recall of *autobiographical* episodic memories from an individual's life history. A further limitation of this evidence base is the negative symptom measures used such as the Positive and Negative Syndrome Scale (Kay, Fiszbein et al. 1987) and the Scale for the Assessment of Negative Symptoms (Andreasen 1984). These have been criticized for not accurately discriminating between current and anticipated pleasure and motivation (Messinger, Tremeau et al. 2011, Edwards, Cella et al. 2015). There is also a very mixed evidence base as to whether these older measures overlap significantly with the measurement of depressive symptoms in people with schizophrenia (Blanchard, Horan et al. 2001, Kollias, Kontaxakis et al. 2008). Indeed, over-general memory has a well-established role in the symptoms of depression and subsequent reduced functioning (Williams, Barnhofer et al. 2007) and it is not clear from the existing evidence whether memory impairments may be linked to depressive symptoms in psychosis. Recent studies in depression have also considered the importance of memory *flexibility*, specifically that it may be adaptive to generalise autobiographical positive memories and keep negative memories specific and clearly bounded (Hitchcock, Mueller et al. 2016). This emphasises the importance of considering the valence of the memory being retrieved which may therefore have a different relationship to negative or depressive symptoms.

To improve the effectiveness of cognitive-behavioural therapies for psychosis, an interventionist-causal method is recommended (Freeman 2011). The premise of this approach is to focus on one causal mechanism, demonstrate whether it can be altered and then examine the effect on the target symptoms. For example, the causal role of worry and reasoning biases in paranoia has been demonstrated, and interventions targeting these processes show promise (Freeman, Dunn et al. 2015, Garety, Waller et al. 2015). This study will therefore employ a causal interventionist approach to investigating the potential causal role of autobiographical episodic memory in negative symptoms. The current evidence base includes two intervention studies. The first targeted the specificity of episodic memory in people with psychosis and was conducted in a group format; participants ( $n = 24$ ) were encouraged to keep diaries with specific daily memories and their associated emotions, this was then extended to more historical memories from childhood, adolescence and adulthood. The intervention improved memory specificity but there was no subsequent improvement in symptoms, although they were assessed using older measures and the group was not selected for negative symptoms (Ricarte, Hernández-Viadel et al. 2012). Another study targeted the potential causal link between over-general memory and negative emotions about future events in 32 participants with schizophrenia-spectrum diagnoses. The results showed that recalling a memory in response to event-related cues such as "birthday" or "argument" before completing a prospective task enhances positive mood when anticipating the future activity (Painter and Kring 2016).

The evidence reviewed so far suggests that impairments in episodic memory may contribute to negative symptoms and/or depression in people with schizophrenia. However, findings are somewhat equivocal which may be attributable to the limitations of negative symptoms and episodic memory measures, and small sample sizes. Robust investigation of the potential causal mechanism of episodic memory impairments in negative symptoms is important because they are a potential treatment target in an area with very few evidence-based interventions and a large unmet need. The outcomes to be investigated in this intervention study will be positive affect, negative affect, motivation and anticipatory pleasure as these have been identified as important components of negative symptoms and used in similar previous studies (Sanchez, Lavayssse et al. 2014, Edwards, Cella et al. 2015, Painter and Kring 2016). A measure of self-efficacy will be added as a novel outcome measure as this has recently been highlighted as a potential causal mechanism in negative symptoms and poor functioning (Campellone, Sanchez et al. 2016).

